6.2.1. Changes to the analyses planned in the study protocol

	are planned as part of this SAP.	protocol writing. Such an analysis
	Subjects are summarized by pooled	would not be interpretable.
	dose groups (based on first	-
	randomized dose of ponesimod)	
	only.	
5.3	For ARR, it is stated that "In	"Number of documented relapses in
	addition, the treatment effect on	a fixed 24-month period cannot be
	aggregate ARR will be tested by	determined for ponesimod baseline
	means of negative binomial	(of placebo switchers) and so the
	regression adjusted by treatment,	value prior to start of the core is
	region, number of documented	used. The categories are modified
	relapses (≤ 2 and > 2) past 24	as only a very small proportion of
	months prior to screening, EDSS	subjects would fall into $a > 2$
	[Expanded Disability Status Scale]	category.
	at baseline (CRF Visit 2) and total	EDSS is categorized as the log-rank
	number of T1 Gd+ [gadolinium-	test (which is displayed alongside
	enhancing] lesions at baseline." This	the Cox regression results) can only
	is similarly applied for the Cox	take categorical variables as
	proportional-hazard regression	covariates. Given the small sample
	model for time to first relapse, and	size only the two more important
	negative binomial model for MRI	covariates are selected.
	endpoints.	The same two covariates are used
	Only two covariates will be included	for all adjusted analyses (i.e., also
	in the adjusted models: EDSS score	for the negative binomial model for
	category (≤ 3.5 and > 3.5) based on	ARR and MRI) for consistency.
	extension baseline, and relapses in	
	the 2 years prior to screening in the	
	core study (≤ 1 and ≥ 2).	
	EDSS is defined as a categorical	
	variable. Number of documented	
	relapses categorization is modified	
5.2	$\frac{1}{100} \le 2 \text{ and } \ge 2^{\circ} \text{ to } \le 1 \text{ and } \ge 2^{\circ}.$	T1
5.5	It is stated that "Different methods	I ne interim analysis covers a period
	data and to nonform consistivity	of almost 9 years and higher drop-
	and to perform sensitivity	long pariod Imputation of missing
	a result of missing information. The	data over this long of a period would
	methods will include an analysis	be difficult to interpret
	which treats missing values as a	be difficult to interpret.
	success and an analysis which treats	
	missing values as a failure "	
	These sensitivity analyses are not	
	planned in this SAP for some of the	
	endpoints.	
5.4	The dose response relationship will	Without a placebo arm only
	be explored for lymphocyte count	represents less than 10% of the
	MRI related endpoints (number of	follow-up for patients originally
	total T1 Gd+ lesions, number of	randomized to placebo so for reason

	combined unique active lesions, number of new or enlarging T2 lesions) and ARR using modeling techniques as described by Bretz et al [Bretz 2005]. This modeling is not planned in this SAP.	previously discussed placebo is being excluded from the analysis. MCP-Mod without a placebo (0 dose) makes the analysis difficult to interpret. Dose response was instead summarized in a more descriptive manner.
5.6	It is stated that "AEs, SAEs, and abnormalities are defined as treatment-emergent when occurring during study drug administration plus 7 days after study drug discontinuation.". The definition of treatment- emergent is updated to 15 days after last study drug administration in this SAP.	15 days is consistent with the Phase 3 program.
5.6	It is stated that "In addition, AEs of clinical interest will be summarized by the dose the patient received as per-protocol at time of onset.". This summary is not planned in this SAP.	Due to the potential carry over effect when subjects switch from one ponesimod dose to another, AEs will not be summarized by dose at onset.
3.10.1	Appendix 11: Planned Covid-19 analyses	Added to address efficacy endpoint No. 8 related to Covid-19 vaccine in Protocol Amendment 11.
2	Section 1.1: Objective: To explore the dose response relationship of 10, 20, and 40 mg ponesimod on lymphocyte count, magnetic resonance imaging (MRI) endpoints, annualized relapse rate (ARR), and safety endpoints	This objective was addressed in the Interim Analysis CSR in 2019 and will not be further addressed in the Final CSR.
5.1.9	Section 5.1.9 Analysis Strategy for long term efficacy and safety	Only AP3 will be considered for the Final CSR as it encompasses the entire ponesimod treatment period. Further, AP1 and AP2 were addressed in the Interim Analysis CSR in 2019.
3.10.1	Appendix 12: Influenza Analyses	Added to address efficacy endpoint No. 8 related to influenza vaccine in Protocol Amendment 11.
	Section 5.5.8. Added Covid-19 Impact Analyses in SAP.	This analysis was deemed important to assess due to the pandemic that occurred while the study was ongoing.
	Section 5.5.9 Added Regional Crisis	This was deemed important to
	Impact Analyses in SAP.	assess due to the regional crisis that

CONFIDENTIAL – FOIA Exemptions Apply in U.S.

Status: Approved, Date: 20 September 2023

	occurred while the study was
	ongoing.

6.2.2. Changes in the conduct of the study / data collection

None.

6.2.3. Clarifications concerning endpoint definitions and related variables or statistical methods

Protocol section	Change	Rationale
3.10.2.5	Regarding the bronchodilator assessment, it is stated that "This assessment is mandatory and will be performed at Visit P1 and on a yearly basis during TP1 and TP2. During TP3 bronchodilator test is recommended to be continued on a yearly basis (as deemed necessary by the investigator)." In fact, the bronchodilator assessment was not performed in TP1 at all and was only introduced at the start of TP2 (Visit P1).	Clarification.
3.9.1	It is stated that the endpoint "Time to 12- week confirmed disability progression up to end of the study" will be evaluated. This will not be done.	As EDSS is only scheduled every 24 weeks in TP1, it is not possible to determine time of 12-week CDA [Confirmed disability accumulation] during this period. Therefore only "Time to 24-week confirmed disability accumulation" was evaluated.
3.9.1	It is stated that the endpoint "Categorical change from baseline to all assessments in EDSS and FS [functional system] scores" will be evaluated. This will not be done.	This endpoint was evaluated in the core study as categorical change from baseline to Week 24, where categorical change is classed as stable, improved or worsening at Week 24 as compared to baseline. Due to the long running nature of the extension study and lack of defined endpoint, this endpoint will not be defined in the extension study.
3.9.1	It is stated that the safety and tolerability endpoints "Change in ophthalmological exam (best corrected visual acuity, low contrast visual acuity, visual fields, dilated	These safety ophthalmological data are assessed at site but not collected on the CRF.

	ophthalmoscopy, and at selected centers, OCT [optical coherence tomography]) from baseline to all assessments" will be derived. This will not be done.	
3.9.1	It is stated that the endpoints "Change in laboratory parameters (hematology, blood chemistry, and urinalysis) from baseline to all assessments" will be derived. This will be done for hematology and blood chemistry parameters, but not for urinalysis.	Urinalysis is performed locally, and results are not collected on the CRF.
AC- 058B201 CSR SAP section 6.4.3.1	The EDSS assessment used for confirmation of disability accumulation must not be during a relapse. In the event of a missing relapse end date, the core study report considered relapse start date + 30 days. This SAP uses relapse start date + 90 days.	This derivation is updated to be in-line with the deviation as used in the Phase 3 program.
Section 5.1.3	Definition of Treatment emergent adverse events and other safety variables.	Definition updated to exclude pregnancy interruption period(s).
Various Sections	Disposition will include a new category corresponding to "Approved drug available for indication".	New reason in aCRF p.9 (Trial disposition) and p. 11 (Discontinuation of Study Treatment): "Approved drug available for indication".
Section 5.4.5.4		Echocardiogram: Criteria for defining abnormality have changed subsequent to 2019 IA and are reflected in the SDTM data.
Section 5.1.7	Coding Dictionaries: MedDRA Version 26.0 and WHO-Drug Dictionary version March 2023 B3G will be used.	Up-versioning to current dictionaries.
Section 5.1.3	Added Planned Pregnancy Interruptions: - excluded for definition of exposure, treatment-emergent adverse events and other safety variables. - not excluded for efficacy analyses or for study duration.	This rule was adopted for the Snapshot Analysis in 2022 and will be retained for the Final CSR.
Section 5.1.6	Added Definition: The post-treatment- emergent period.	This period was added to address analyses pertaining to relapses in Section 5.3.1.4 and for AEs in Section 5.4.4.3.3.

Section 5.1.8	Added additional Visit Windows	Added to cover the entire study period.
Section 5.2.1.3	Added Definition: Entered Follow-up Phase.	This definition is required for the identification of patients in the DMT subgroups.
5.2.2	Display of Subject Disposition: Kaplan- Meier plot for time to premature treatment discontinuation will not be presented.	This was presented in the Interim Analysis CSR and will not be presented in the Final CSR.
5.3.1.2	Removed Analyses for the endpoint: ARR up to last treatment in the Analysis Period + 7 days will not be performed.	This was presented in the Interim Analysis CSR and will not be presented in the Final CSR.
5.3.1.4	Added endpoint in Section 5.3.1.4: Annualized relapse rate in the Post- treatment-emergent period. Added planned analyses for this endpoint in Section 5.3.2.2.	This was added to assess disease reactivation.
5.3.1.5	Explanation added regarding the response to the question about relapse requiring hospitalization.	To address the discrepancy between the response "Yes" to the question in the legacy CRF and the question in RAVE.
5.3.2.1	Removed the presentation of p-values in this section; and elsewhere in the SAP.	All exploratory analyses.
5.3.2.4	Removed Sensitivity analyses for ARR	This was presented in the Interim Analysis CSR and will not be presented in the Final CSR.
5.3.2.5	Removed Sensitivity analyses for Time to first confirmed relapse	This was presented in the Interim Analysis CSR and will not be presented in the Final CSR.
5.3.3.3	Added endpoint definition: Combined unique active lesions (CUAL) at each timepoint	This was deemed important to assess.
5.3.4.1	Removed Analyses for the cumulative total number of T1 Gd+ lesions	This was deemed not important to address in the Final CSR. Instead this analysis will be conducted for CUALs.
5.3.4.1	Removed Sensitivity analyses for T1 Gd+ lesions.	This was presented in the Interim Analysis CSR and will not be presented in the Final CSR.
Statistical Analysis Plan AC-058B202

5.3.4.2	Removed Analyses for the cumulative total number of T2 lesions	This was deemed not important to address in the Final CSR. Instead this analysis will be conducted for CUALs.				
5.3.4.2	Removed Sensitivity analyses for T2 lesions.	This was presented in the Interim Analysis CSR and will not be presented in the Final CSR.				
5.3.4.3	Added analyses for the number of CUALs per MRI time window	This was deemed important to assess.				
5.4.3.2	Added definition for Post-treatment adverse events	Definition required for table of post- treatment AEs.				
5.4.4.1	Removed Summaries of AEs with onset on Day 1	This was presented in the Interim Analysis CSR and will not be presented in the Final CSR.				
5.4.4.4	Removed outputs related to Treatment emergent AEs with onset of Day 1 of first ponesimod or Day 1 of any re-initiation	This was presented in the Interim Analysis CSR and will not be presented in the Final CSR.				
	Removed Time to first treatment- emergent AESI for each AESI category for AP3, using the Kaplan-Meier method	This was presented in the Interim Analysis CSR and will not be presented in the Final CSR.				
5.4.5	Only marked Laboratory abnormalities as defined in Appendix 8, and specified ECG, BP and liver function abnormalities will be presented in listings. However all lymphocyte values will be presented.	Given the long duration of the study, this was considered a reasonable approach As lymphocyte counts are a PD marker, all values will be presented.				
5.4.5.1	Modified analyses for lymphocytes outputs related to ponesimod baseline, at last on-treatment and at each follow-up visit by Post-Treatment DMT subgroup.	This was deemed important to assess.				
5.4.5.1	Added plot to evaluate Drug-Induced Serious Hepatotoxicity (eDISH plot)	This was deemed important to assess.				
5.4.5.1	Urinalysis results were to be collected and recorded only if an abnormality/ finding would constitute an (S)AE.	The limited number of available data does not allow for performing the planned analyses				
5.4.5.2.1	Removed outputs for Blood Pressure: Pre-dose values on Day 1, Day 8 and Day 15 following first ponesimod administration and on Day 1 of re- initiation.	This was presented in the Interim Analysis CSR and will not be presented in the Final CSR. This was deemed important to assess.				

CONFIDENTIAL – FOIA Exemptions Apply in U.S.

Statistical Analysis Plan AC-058B202

	Added: Summary for blood pressure abnormalities	
5.4.5.1	Modified: Lab Listings will only be produced for abnormal values	Given the long duration of the study, lab listings will be restricted to abnormal values only.
5.4.5.3	Electrocardiogram: Removed outputs related to ECG parameters on nominal Day 1, 8 and 15 relative to first ponesimod administration. Removed outputs related to incidence of treatment-emergent abnormalities, as well as PR and QTc prolongations.	This was presented in the Interim Analysis CSR and will not be presented in the Final CSR.
5.4.5.5	Modified analyses for PFT outputs related to ponesimod baseline, at last on- treatment and at each follow-up visit by Post-Treatment DMT subgroup. Added outputs based on Total Exposure Duration Subgroup.	This was deemed important to assess.
5.5.1	Added outputs related to Pharmacokinetics	This section was added to analyze the plasma concentration data collected in the study.
5.5.2	Link to outputs for lymphocytes that addressed the pharmacodynamic marker in the study.	The pharmacodynamic marker in the study was lymphocytes.
5.5.3	Pharmacokinetic/Pharmacodynamic Relationships	Analyses to address dose decisions were presented in the Interim Analysis CSR and will not be addressed in the Final CSR
5.5.6	Added definitions of subgroups Post- treatment DMT and Total Exposure Duration.	These subgroups were added to address the need for outputs based on the subgroups in the post- treatment-emergent period.
6.4	Only major PDs will be presented	Given the duration of the study. Also important PDs were a definition used in the legacy CRF and have been mapped to eCRF.
6.5	Definition of Treatment-concomitant therapies modified from "that were initiated up to 15 days after the end of ponesimod treatment to " that were	To ensure consistency with the definition of Post-treatment DMT subgroup.

	initiated upto the end of ponesimod treatment".	
6.5.1	Table 11 includes some medications that are not DMTs (etrasimod, sekukinumab), but will be retained for consistency with IA outputs.	
6.5	CMCLASS for Covid Vaccines updated	Updated based on current dictionaries.
6.8	Appendix 9 AESIs	Updated AESIs based on current coding dictionaries.

6.3. Appendix 3 Demographics and Baseline Characteristics

6.3.1. Demographics

Demographic data are collected at entry into the core study only. Demographic data include country, age, sex, race, weight and height. Date of birth is not available, and as the core study duration was only 6 months, age at start of extension is assumed to be the same as age at the start of the core. All demographic variables are stored in SDTM201.DM.

Age categories are derived from the above as follows: <18, 18-30, 31-40, 41-55, \geq 56 years. Age high-level categories: <40, \geq 40. Age categories as per EudraCT requirement: < 12 years, 12 - 17, 18 - 64, 65 - 84, \geq 85.

Two categorizations are derived for region. The first categorization reflects the regions as they were defined in the core study report, with the following regions defined:

- Northern/Western Europe: Finland, Sweden, Belgium, Netherlands, Germany, UK, and Poland;
- South/Central Europe: Austria, France, Italy, Spain, Switzerland, Hungary, and Czech Republic;
- Eastern Europe / Israel: Bulgaria, Israel, Romania, Serbia, Russian Federation, and Ukraine;
- North America / Australia: USA, Canada, and Australia.

The second categorization is consistent with the Phase 3 program. The following regions are defined:

- European Union (EU) + UK + Switzerland: Austria, Belgium, Bulgaria, Czech Republic, Finland, France, Germany, Hungary, Italy, Netherlands, Poland, Romania, Spain, Sweden, Switzerland, and United Kingdom;
- Europe Non-EU + Russia: Russian Federation, Serbia, and Ukraine;
- North America: Canada, and United States;
- Rest of World: Australia, and Israel.

Region categorizations are based on the region of the site the subject was in at the start of the core study. Site changes that result in region changes are not considered.

Demographic characteristics are summarized using descriptive statistics for continuous and categorical data, by treatment group and overall for the PAS.

6.3.2. Baseline disease characteristics

The following baseline disease characteristics are collected at entry into the core study and analyzed as part of this SAP:

• Number of documented relapses within 12 months and within 24 months prior to screening in core study.

This variable cannot be determined prior to start of the extension study as not all the dates of precore relapses were collected (only the most recent).

The following baseline disease characteristics are derived relative to ponesimod baseline:

- Time (years) since first Multiple Sclerosis (MS) symptoms defined as ponesimod start date date of first MS symptom;
- Time (years) since MS diagnosis defined as ponesimod start date date of MS diagnosis;
- Time (months) since the most recent documented relapse prior to first dose of ponesimod defined as ponesimod start date date of most recent documented relapse prior to ponesimod start date (including relapses in the core study for subjects randomized to placebo);
- Expanded Disability Status Scale (EDSS) score at ponesimod baseline, continuous and categorical (0, 1.0, 1.5, 2.0, 2.5, 3.0, 3.5, 4.0, 4.5, 5.0, 5.5, > 5.5);
- Number of T1 Gadolinium-enhancing (Gd+) lesions at ponesimod baseline;
- Proportion of subjects with at least one T1 Gd+ lesion at ponesimod baseline;
- Total volume of T2 lesions at ponesimod baseline.
- Number of documented relapses within 12 months and within 24 months prior to screening in the core study. A footnote in the tables should be added explaining that these are prescreening rates.

See Section 5.1.1 for definition of ponesimod start date and Section 5.1.2 for definition of ponesimod baseline.

Baseline disease characteristics relative to ponesimod baseline are summarized using descriptive statistics for continuous and categorical data, by treatment group and overall for the PAS.

6.4. Appendix 4 Protocol Deviations

Protocol deviations are all those recorded in the database following the specifications provided in the protocol deviation code list. No major deviations are defined and no deviations lead to exclusion from the analysis sets.

All major protocol deviations recorded during the extension study are summarized by category, by treatment group and overall.

A listing of major protocol deviations (coded term, reported term) recorded during the extension study is provided.

Protocol deviations are summarized and listed for the PAS, subset on those subjects who entered the extension study only.

6.5. Appendix 5 Prior and Concomitant Medications

Previous and concomitant medications/therapies are stored in the SDTM.CM datasets. The two CM datasets SDTM201.CM and SDTM202.CM are concatenated for the purposes of this analysis. Terms are coded using the World Health Organization (WHO) drug code dictionary and the anatomic therapeutic chemical (ATC) class code (version dated September 2021 B3G).

A previous therapy is any treatment for which the end date of treatment is prior to the first dose of ponesimod (including medications with an end date in the core study for patients originally randomized to placebo).

Treatment-concomitant therapies are all treatments that are ongoing or initiated after first dose of ponesimod, or that were initiated up to the end of ponesimod treatment.

Post-treatment therapies are those which were initiated after the end of ponesimod treatment, i.e after the ponesimod EOT date as described in Section 5.1.1

Where start date of medication/therapy is missing or partial, the following medications/therapies are considered to be previous therapies:

- Medication end date is not missing and is < ponesimod treatment start date;
- If day is missing and the month/year of the medication end date is < month/year of the ponesimod treatment start date;
- If day and month are missing and the year of the concomitant medication end date is < year of treatment start date.

Otherwise, the medications/therapies with missing or partial start date are considered as treatmentconcomitant. Medications considered treatment-concomitant where there is a possibility that they are previous will be flagged in listings, for example, if day is missing and month and year are same as month and year of ponesimod start date.

Beta blocking therapies will be listed for the pooled B201/B202 studies. Beta blocking agents are defined as medications with WHO-Drug anatomic therapeutic chemical (ATC) class level 2 code C07: BETA BLOCKING AGENTS". This is a sub-class of ATC class C "Cardiovascular system". Steroids used for the treatment of relapses are selected in SDTM.CM using CMCAT="CORTICOSTEROIDS (IV) FOR TREATMENT OF RELAPSE".

Covid-19 vaccines are selected in SDTM.CM using CMCLASS = "COVID-19 VACCINES".

Assignment as prior, treatment-concomitant, and post-treatment therapy is derived using the definitions above.

An additional flag for therapies taken during planned pregnancy interruption will be derived and will include all therapies that started after last intake prior to pregnancy interruption + 15 days and stopped prior to the re-initiation date of study treatment after planned pregnancy.

A therapy with missing or partial start date will not be flagged as taken during planned pregnancy interruption.

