3.4.4.2 Allowed concomitant medications

Administration of intravenous (i.v.) atropine in the event of symptomatic bradycardia.

Vaccination with non-live vaccines is allowed while on study treatment if the vaccination is advised by the primary investigator / treating neurologist, based on her/his clinical assessment of the risk/benefit for the individual patient, and if supported by guidelines for vaccination relevant to this patient population, as applicable.

Ponesimod / ACT-128800 / JNJ-67896153 Multiple Sclerosis		EudraCT 2009-011470-15 EDMS-ERI-206617631
Protocol AC-058B202	Confidential	
Version 12		
15 March 2022, page 63/179		

Patients receiving non-live vaccination against influenza or COVID-19 while on study treatment will have 5 mL of blood drawn prior to and at least 3 weeks after vaccination in order to explore changes in vaccine-specific antibody titers from pre- to post vaccination. Samples will be analyzed at the end of the study at the latest. In case of a vaccine requiring the administration of multiple doses, the post-vaccination sample should be collected at least 3 weeks after the administration of the last dose.

Glatiramer acetate and IFN β -1a are allowed only during study drug interruptions for planned pregnancy. These treatments may be started 7 days after study drug interruption and must be stopped 7 days before study drug re-initiation.

Low dose of corticosteroids (up to 10 mg of prednisone equivalent daily), given as shortterm treatment (up to 2 weeks per treatment cycle with at least 8 weeks' interval between treatment cycles and no more than 4 weeks per year of the study duration on average), and inhaled corticosteroids for pulmonary conditions.

Other treatments considered necessary for the patient's benefit and not categorized as prohibited concomitant medications.

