3.11.5.3 Concomitant medications

All medications taken by the patient from the beginning of the transition period until EOS2 or EOS3, i.e., all medications ongoing, started or stopped during this period, will be recorded on the Concomitant Medications form of the extension eCRF.

Commercially available ponesimod may be initiated on the day following last intake of study treatment. The start date of commercially available ponesimod must be recorded on the Concomitant Medication form of the eCRF.

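### SAP 6.5 does not cap concomitant therapy at end of ponesimod treatment as its change log intends, and its pregnancy-interruption flag misses bridging drugs the protocol already permits

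*SAP*

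**What the plan says.** SAP 6.5 (Appendix 5) sorts therapies into three classes by date.

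- Previous: "A previous therapy is any treatment for which the end date of treatment is prior to the first dose of ponesimod".
- Treatment-concomitant: "all treatments that are ongoing or initiated after first dose of ponesimod, or that were initiated up to the end of ponesimod treatment".
- Post-treatment: "Post-treatment therapies are those which were initiated after the end of ponesimod treatment".

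The section adds: "Assignment as prior, treatment-concomitant, and post-treatment therapy is derived using the definitions above". It gives no order of precedence and does not say that the classes exclude one another.

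The change log in SAP 6.2.3 records that the concomitant window used to run to 15 days after the end of ponesimod and now stops at the end of ponesimod. The reason given is consistency with the Post-treatment DMT subgroup.

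SAP 6.5.1 classes DMTs as previous or concomitant under the 6.5 definitions and summarizes those two groups in their own tables. Table 11, the DMT list, contains ponesimod, glatiramer acetate and interferon beta-1a. Protocol 3.11.5.3 lets commercial ponesimod begin the day after the last study dose and says "The start date of commercially available ponesimod must be recorded on the Concomitant Medication form of the eCRF".

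SAP 6.5 also derives an extra flag for drugs taken during a planned pregnancy interruption. It "will include all therapies that started after last intake prior to pregnancy interruption + 15 days and stopped prior to the re-initiation date". Protocol 3.4.4.2 allows glatiramer acetate and interferon beta-1a during such interruptions: "These treatments may be started 7 days after study drug interruption".

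**The concern.** There are two separate defects.

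**The class has no working boundary.** One alternative (started after first dose) has no upper limit, and another (started by the end of treatment) has no lower limit. Joined by *or*, they admit everything. A DMT begun after study drug ended would count both as post-treatment and as concomitant. The DMT tables name only two classes, so such a drug has no other place to go there. The SAP's Introduction assigns this programming to a CRO, so the written rule is what will be coded unless someone asks.

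**The flag starts later than the permitted bridging.** Protocol 3.4.4.3 prohibits these immunomodulators except during a planned pregnancy interruption. An unflagged course therefore looks like a prohibited drug taken on ponesimod. Identification also matters because SAP 5.1.3 keeps planned pregnancy interruptions in the efficacy analyses. Relapses and EDSS scores recorded on a bridging DMT count towards ponesimod, and this flag is the SAP's marker for drugs taken in those intervals.

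What is at stake is whether the concomitant-DMT table describes drugs taken alongside ponesimod, and whether bridging courses can be picked out.

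**Working it through.** The plan gives no figure to reproduce, so the check applies the rules as written.

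**1. The concomitant rule.** Let F be the first ponesimod dose, E the EOT, and s and e the start and end of a therapy. As written:

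concomitant = (s ≤ F and e ≥ F) or (s > F) or (s ≤ E).

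F is never later than E, so every start date satisfies s > F or s ≤ E. The rule is therefore true for every dated therapy. With the cap that the change log describes:

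concomitant = (s ≤ F and e ≥ F) or (F < s ≤ E).

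**2. The flag.** Let L be the last intake before the pregnancy interruption and R the re-initiation date. As written:

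flag = (s > L + 15) and (e < R).

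The first start day that can be flagged is L + 16. Counting the protocol's 7 days from the last intake, permitted starts on days 7 to 15 are missed: 15 − 7 + 1 = 9 days. Counting from the first missed dose, the missed starts are days 8 to 15: 15 − 8 + 1 = 8 days.

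**3. Test cases.** The dates are hypothetical: F = 0, L = 1000, R = 1500, E = 3000. Bridging stops at 1493, which is 7 days before R as the protocol requires.

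| Therapy (start, end) | Previous | Concomitant as written | Concomitant with cap | Post-treatment | Flag |
|---|---|---|---|---|---|
| Ended before first dose (−500, −100) | yes | yes | no | no | no |
| Ongoing at first dose (−50, 30) | no | yes | yes | no | no |
| Started on treatment (200, 300) | no | yes | yes | no | no |
| Started day after EOT (3001, 3060) | no | yes | no | yes | no |
| Bridging from day 7 (1007, 1493) | no | yes | yes | no | no |
| Bridging from day 15 (1015, 1493) | no | yes | yes | no | no |
| Bridging from day 16 (1016, 1493) | no | yes | yes | no | yes |

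Rows 1 and 4 show the double classification. Row 4 is the date pattern of commercial ponesimod.

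**4. Does the flag change the table?** No. For a patient who restarts, F < L + 7 and R ≤ E, so any bridging start lies between F and E. The last three rows are concomitant under both readings, and only the flag column differs.

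**5. The replacement rule.** Take concomitant as (e ≥ F or ongoing) and (s ≤ E). Previous is e < F, which excludes concomitant. Post-treatment is s > E, which also excludes it. A therapy with s > E cannot have e < F. The three classes then cover every dated therapy exactly once.

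**The case against.** The strongest reply is that nobody would code the sentence literally. A rule that makes everything concomitant would leave the other two classes pointless. The neighbouring sentence defines post-treatment therapy, the subject listings carry all three labels, and the change log states the EOT bound with its reason. On that reading commercial ponesimod is plainly post-treatment. This stands as far as intent goes: the intended cap is recoverable. It does not cure the text, because no precedence is stated and the DMT summaries in SAP 6.5.1 name only two classes.

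On the flag, the 15 days have a source. SAP 5.1.4 keeps the first 15 days after the last pre-pregnancy dose in the treatment-emergent period and starts the pregnancy-interruption period at day 16. That is a sound safety window for adverse events. It does not mark when a bridging drug may begin, and the same change log shows the sponsor removing a 15-day extension from the concomitant definition in this very section.

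The impact is also limited. The tables are descriptive and show drugs by preferred term. Major protocol deviations are summarized and listed separately. The Post-treatment DMT subgroup in SAP 5.5.6 uses its own date rule. No efficacy or safety estimate in the SAP is shown to depend on the concomitant class. All of that stands.

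**Conclusion.** Both defects hold and should be corrected. The first depends on reading the sentence as written: previous and post-EOT therapies then fall into the concomitant class, against the sponsor's recorded intent. The second needs no such assumption: permitted bridging starts on 8 or 9 days, depending on how day 7 is counted, cannot be flagged.

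A reader might infer more than the documents support in two respects.

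- **That the late flag lets bridging DMTs into the concomitant-DMT table.** It does not. The flag is additional and excludes nothing. All bridging DMTs in patients who restart are counted in that table whatever day they began, so an earlier flag alone would remove none of them.
- **That DMT use alongside ponesimod will look greatly inflated.** The documents give neither the number of DMT starts after EOT nor the number of pregnancy interruptions, so no percentage can be attached. The share of bridging courses missed could be anything from none (all begun after day 15) to all (all begun on the earliest permitted day).

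The consequence is a mislabelled descriptive table and incomplete identification of bridging drugs, in a study whose objectives are all exploratory.

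**What to change.** 1. Define treatment-concomitant as an end date on or after the first ponesimod dose (or ongoing) **and** a start date on or before ponesimod EOT. State that previous, concomitant and post-treatment are mutually exclusive, and apply all three to DMTs in SAP 6.5.1.
2. Start the medication flag after the last intake before the pregnancy interruption. Leave the 15-day treatment-emergent window for adverse events in SAP 5.1.4 as it is. This changes only the analysis flag; the protocol's rule on when bridging may begin is not in question.
3. Show flagged DMTs separately from the concomitant-DMT counts, since moving the flag alone does not change those counts.

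The cost is a few sentences in SAP 6.5 and 6.5.1 and a revised derivation. The start and end dates are already recorded, so no new data are needed.
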